Return of eDiary devices or removal of eDiary application from participant personal device																		○			
Recording of unsolicited events (Days 1-31) post-Dose 1 and post-Dose 2 of study intervention administration		●	●	●	●	●	●	●	●	●	●	●	●	●	●	●	●	●	●	See Section 10.3.8 for more information	
Recording of SAEs, MAEs, pIMDs and pregnancies		●	●	●	●	●	●	●	●	●	●	●	●	●	●	●	●	●	●	See Section 10.3.8 for more information	
Recording of SAEs related to study participation, or to a concurrent GSK medication/vaccine	●	●	●	●	●	●	●	●	●	●	●	●	●	●	●	●	●	●	●	See Section 10.3.8 for more information	
Recording of AEs/SAEs leading to withdrawal from the study		●	●	●	●	●	●	●	●	●	●	●	●	●	●	●	●	●	●	See Section 10.3.8 for more information	
Study Conclusion																				●	See Section 4.5 for more information

V = visit; PC = phone contact; D = day; HBs = Hepatitis B surface antigen; HBc = Hepatitis B core antigen; CMI = cell-mediated immunity; eDiary = electronic diary; SAE = serious adverse event; MAE = medically attended event; pIMD = potential immune-mediated disorder; AE = adverse event; eCRF = electronic case record form; CCI [REDACTED]

CCI [REDACTED].

Note: The double-line border following Day 61 indicates the main analyses that will be performed on all data (i.e., data that are as clean as possible) obtained up to Day 61.

● is used to indicate a study procedure that requires documentation in the individual eCRF.

○ is used to indicate a study procedure that does not require documentation in the individual eCRF.

CONFIDENTIAL

215301 (EARLY-CLINRES-017)
Protocol Amendment 4 Final

1Only for participants in the HBs-alum group.

2Note: Participants with anti-HBs Ab concentration < 100 mIU/mL at Day 361 will be offered a dose of *Engerix-B* after the study.

CCI

[figure not shown]

Table 2 Intervals between study visits

Interval	Optimal length of interval ¹	Allowed interval ²
Screening Visit → Visit 1	7 days	2-28 days
Visit 1 → Visit 2*	1 day	1 day
Visit 2 → PC1	2 days	2 days
PC1 → PC2	2 days	2 days
Visit 1 → Visit 3	7 days	7-8 days
Visit 3 → PC3	2 days	2 days
PC3 → PC4	2 days	2 days
PC4 → PC5	3 days	3 days
Visit 1 → Visit 4	30 days (1 month)	21-42 days
Visit 4 → Visit 5*	1 day	1 day
Visit 5 → PC6	2 days	2 days
PC6 → PC7	2 days	2 days
Visit 4 → Visit 6	7 days	7-8 days
Visit 4 → Visit 7	30 days (1 month)	21-42 days
Visit 4 → Visit 8 ³	150 days (5 months)	136-164 days
Visit 6 → PC8	2 days	2 days
PC8 → PC9	2 days	2 days
PC9 → PC10	3 days	3 days

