Visit 7 → Visit 9 ⁴	300 days (10 months)	286-314 days
Visit 8 → Visit 9 ³	180 days (6 months)	166-194 days

PC = phone contact

¹Whenever possible the investigator should arrange study visits within this interval.

²Participants will not be eligible for inclusion in the Per-Protocol Set for analysis of immunogenicity if they make the study visit outside this interval.

³For participants in the HBs-alum group.

⁴For participants in all groups except the HBs-alum group.

CCI

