3. OBJECTIVES AND ENDPOINTS

Table 3 Study objectives and endpoints

Objectives	Endpoints	Primary
To evaluate the reactogenicity and safety in all study groups.	
 Percentage of participants with solicited administration site and systemic AEs within 14 days (Day 1 till Day 14) after Dose 1 and Dose 2. Duration of solicited AEs (administration site and systemic) after Dose 1 and Dose 2. Percentage of participants with any unsolicited AEs within 31 days (Day 1 till Day 31) after Dose 1 and Dose 2. Percentage of participants with SAEs, MAEs and AEs leading to study withdrawal throughout the entire study period. Percentage of participants with pIMDs throughout the entire study period. The absolute values and changes in hematology and biochemistry parameters post-Dose 1 (Day 8 and Day 31) and post-Dose 2 (Day 38 and Day 61) from baseline (pre-vaccination, Day 1). 	

CONFIDENTIAL

215301 (EARLY-CLINRES-017)

Protocol Amendment 4 Final

Objectives	Endpoints
	
 Percentage of participants with abnormal laboratory parameter values at pre-vaccination (Day 1), post-Dose 1 (Day 8 and Day 31) and post-Dose 2 (Day 38 and Day 61).
	Secondary
To evaluate the humoral immune response in all study groups.	
 GMC of Anti-HBs Ab concentrations at Day 1, Day 31, Day 61 and Day 361. Anti-HBs seroconversion and seroprotection rates at Day 31, Day 61 and Day 361.
	Tertiary
CC1	
To evaluate the cell-mediated immune response induced in all study groups.	
 Frequency of HBsAg-specific CD4+/CD8+ T-cells per 10^6 CD4+/CD8+ T-cells producing at least 2 activation markers including at least 1 cytokine among IFN-γ, IL-2, TNF-α, IL-13, IL-17, 4-1BB and/or CD40L at Day 1, Day 8, Day 31, Day 38, Day 61 and Day 361. Frequency of plasmablasts, T Follicular Helper cells (TFH) and memory B-cells (flow cytometry) at Day 1, Day 8, Day 31, Day 38 and Day 61, in a subset of participants.
CC1	
	
 Frequency of HBsAg-specific memory B-cells (ELISPOT) at Day 1, Day 31, Day 61 and Day 361.
CC1	

AE = adverse event; **SAE** = serious adverse event; **MAE** = medically attended event; **pIMD** = potential immune-mediated disorder; **GMC** = geometric mean concentration; **HBs** = Hepatitis B surface antigen; **Ab** = antibody; **CC1** [REDACTED]

[figure not shown]
CC1 [REDACTED]

CC1 [REDACTED]

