4. STUDY DESIGN

4.1. Overall design

Figure 1 Study design overview

CONFIDENTIAL

215301 (EARLY-CLINRES-017)
Protocol Amendment 4 Final

V = visit; **PC** = phone contact; **D** = Day; **N** = number of participants; **SRT** = safety review team; **TP** = timepoint; **CCI** [REDACTED]

Only for participants in the HBs-alum group

ΔPhone contact at Day 4, Day 6, Day 10, Day 12, Day 15, Day 34, Day 36, Day 40, Day 42, and Day 45

*First safety review after the first 5 participants in the HBs-AS37_50 group have completed 7 days safety follow-up post-Dose 1, before administering the second dose to these participants, and before enrolment of the remaining participants in this group in the next cohorts, and the first 5 participants in the HBs-AS37_100 group in the second cohort. The enrolment in the second cohort will start after the second dose is administered to all 20 participants in the first cohort.

**Second safety review after the first 5 participants in the HBs-AS37_50 group have completed 7 days safety follow-up post-Dose 2, before administering the second dose to the remaining participants in this group in the next cohorts.

***Third safety review after the first 5 participants of the HBs-AS37_100 group have completed 7 days safety follow-up post-Dose 1, before administering the second dose to these participants, and before enrolment of the remaining participants in this group in the third cohort. The enrolment in the third cohort will start after the third SRT review.

****Fourth safety review after the first 5 participants in the HBs-AS37_100 group have completed 7 days safety follow-up post-Dose 2, before administering the second dose to the remaining participants in this group in the third cohort.

#Timepoints for safety data cut-off.

CCI

Note: Cohort 3 will enroll a minimum of 70 (and maximum of 105) participants distributed between the groups as follows: a minimum of 23 (and maximum of 30) participants in HBs- Alum, HBs-AS03, HBs-AS04, HBs-AS37_50, HBs AS37_100

- **Type of study:** Self-contained.
- **Experimental design:** Phase 1/2a, dose-escalation, open-label, multi-country study with 5 parallel groups.
- **Duration of the study:** ~ 361 days for all participants.
- **Primary completion date:** Day 361.
- **Control:** Active comparators: *Engerix-B*, *Fendrix* and HBs-AS03.
- **Blinding:** Open-label. Refer to Section [6.4](#) for details.

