- The number and percentage of participants with at least one serious adverse event (SAE) reported any time between the day of vaccination (Day 1) and the end of the study period post vaccination (up to Day 61 for main analysis, up to Day 361 for final analysis) will be classified by MedDRA SOC and PT and tabulated with exact 95% CI. This analysis will be done by group. The same tabulation will be presented for causally related SAEs, fatal SAEs and causally related fatal SAEs.

- The number and percentage of participants with at least one potential immune-mediated disease (pIMD) (selection defined by GSK list of terms AND/OR investigator tick box) reported any time between the day of vaccination (Day 1) and the end of the study period post-vaccination (up to Day 61 for main analysis, up to Day 361 for final analysis) will be classified by MedDRA SOC and PT and tabulated with exact 95% CI. This analysis will be done by group. The same tabulation will be presented for causally related pIMDs.
- The number and percentage of participants reporting each individual pIMD, SAE, or MAE that occurred in the study up to study end/database freeze (DBF) prior to the main analysis will be tabulated and categorized by MedDRA SOC and PT with exact 95% CIs, after each dose and overall. This analysis will be done by group. Note: different groups and doses will have different amounts of follow up time.
- All SAEs/MAEs/pIMD will be described in detail in a tabular listing.
- All AEs/SAEs leading to study/intervention discontinuation from dose 1 up to study end/DBF for main analysis will be tabulated and described in detail in a tabular listing.
- All participants taking concurrent medication/vaccines will be described in a detailed listing.
- For each group and for each hematology and biochemistry parameter, as reported in Table 22 of the study protocol:
  - Comparison of changes since baseline i.e., summary of absolute and relative differences for each parameter by timepoint and by group will be tabulated with descriptive statistics.
  - The number and percentage of participants having hematology and biochemistry results below or above the central laboratory defined normal ranges will be tabulated by timepoint [pre-vaccination (Day1), post-dose 1 (Day 8 and Day 31), post-dose 2 (Day 38 and Day 61)]. This will be done for each group and overall.

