### **6.3.1. Attributing events to vaccine doses**

The dose relative to an event is the most recent study dose given to a participant prior to the start of a given event. For example, if the start date of an AE is between Dose 1 and Dose 2, the relative dose will be Dose 1.

If an event starts on the same day as a study dose, the relative dose will be derived from the additional information provided in the eCRF using the contents of the flag indicating if the event occurred before or after study dose. If 'after study dose' is selected, the relative dose for the event will be the one administered on the start day of the event. If 'before study dose' is selected, the relative dose for the event will be the dose prior to this one.

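### In the final analysis, the post-Dose 2 column of the by-dose SAE, MAE and pIMD table covers about 150 days in HBs-alum and about 330 days in the other four groups, so it is not comparable with the control

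*SAP*

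**What the plan says.** **Primary endpoints.** Protocol Section 3 (Table 3) defines the endpoint for SAEs, MAEs and withdrawal AEs as "Percentage of participants with SAEs, MAEs and AEs leading to study withdrawal throughout the entire study period". The pIMD endpoint has the same scope. SAP 4.2.1 gives MAEs, SAEs and pIMDs their own by-group tables, running from Day 1 to Day 61 at the main analysis and to Day 361 at the final analysis.

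**By-dose breakdown.** A further bullet in SAP 4.2.1 takes each pIMD, SAE and MAE and says that it "will be tabulated and categorized by MedDRA SOC and PT with exact 95% CIs, after each dose and overall", by group, up to study end at the final analysis. The bullet closes with "Note: different groups and doses will have different amounts of follow up time". The visible safety text gives no common window, censoring rule or person-time denominator.

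**Attribution.** SAP 6.3.1: "The dose relative to an event is the most recent study dose given to a participant prior to the start of a given event".

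**Schedule.** Protocol Table 4 and SAP Table 2 give HBs-alum a dose at Visits 1, 4 and 8, and the other four groups a dose at Visits 1 and 4. The footnote to Figure 1 in Protocol 4.1 restricts Visit 8: "Only for participants in the HBs-alum group". The Schedule of Activities places Visit 8 at Day 181. SAP 4.5.1.1 places it at Day 161.

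**The concern.** Under the attribution rule, Dose 3 closes the post-Dose 2 period in HBs-alum. In the other groups nothing closes it before Visit 9. The column headed post-Dose 2 therefore holds raw percentages, each with an exact confidence interval, from periods of very different length. The confidence interval reflects only binomial sampling, so it gives no warning of this.

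The study rationale names the alum-containing control as one of the comparators from which AS37 is to be differentiated. A reader asking what happened after the second dose would look at this column, and it would tend to show fewer events under alum even if the vaccines carried the same risk. The SAP's note shows that the authors saw the unequal time, but a note does not tell the reader how large the effect is or remove it.

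**Working it through.** **Inputs** (Protocol Table 2; optimal interval, then allowed range)
- Visit 1 to Visit 4 (Dose 1 to Dose 2): 30 days (21-42)
- Visit 4 to Visit 7: 30 days (21-42)
- Visit 4 to Visit 8 (Dose 2 to Dose 3, HBs-alum): 150 days (136-164)
- Visit 7 to Visit 9 (two-dose groups): 300 days (286-314)
- Visit 8 to Visit 9 (HBs-alum): 180 days (166-194)

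**Step 1: reproduce the protocol calendar.** Visit 8: 31 + 150 = Day 181. Visit 9: 61 + 300 = Day 361 in the two-dose groups and 181 + 180 = Day 361 in HBs-alum. All agree with the Schedule of Activities.

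**Step 2: post-Dose 2 period at the final analysis.**
- Two-dose groups: 30 + 300 = 330 days; range 21 + 286 = 307 to 42 + 314 = 356.
- HBs-alum: 150 days; range 136 to 164.
- Ratio: 330/150 = 2.2; range 307/164 = 1.9 to 356/136 = 2.6.
- If Visit 8 were at Day 161, as in SAP 4.5.1.1: 161 - 31 = 130 days, ratio 330/130 = 2.5.

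**Step 3: whole-study period.**
- HBs-alum: 30 + 150 + 180 = 360 days (323-400).
- Two-dose groups: 30 + 30 + 300 = 360 days (328-398).

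Nominal follow-up is equal, so the window produces no artefact in the Day 1-361 percentages.

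**Step 4: size of the artefact in the post-Dose 2 column.** Assume the same constant event rate in all groups. The documents give no rate, so a range is shown. P(at least one event) = 1 - exp(-rate × days/365).

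| Rate per person-year | HBs-alum, 150 days | Two-dose groups, 330 days | Ratio |
|---|---|---|---|
| 0.2 | 1 - exp(-0.082) = 7.9% | 1 - exp(-0.181) = 16.5% | 2.1 |
| 0.5 | 1 - exp(-0.205) = 18.6% | 1 - exp(-0.452) = 36.4% | 2.0 |
| 1.0 | 1 - exp(-0.411) = 33.7% | 1 - exp(-0.904) = 59.5% | 1.8 |

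**Step 5: what would be seen at 23-30 per group.** At 0.2 per person-year the expected counts are 23 × 0.079 = 1.8 against 23 × 0.165 = 3.8 participants, or 30 × 0.079 = 2.4 against 30 × 0.165 = 5.0. With independent binomial counts, a given two-dose group would be at or below HBs-alum in 25% (n = 23) or 20% (n = 30) of trials. All four would exceed it in 46% or 53%. At 0.05 per person-year, a given two-dose group would be at or below HBs-alum in 51% or 45%.

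**Step 6: after the fix.** With 150 days in every group, the expected post-Dose 2 percentage at 0.2 per person-year is 7.9% throughout, and the artefact is zero.

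**The case against.** The strongest reply is that the column in question is not the primary endpoint. The primary SAE, MAE and pIMD percentages run over the whole study, have their own tables, and rest on equal nominal follow-up. The by-dose table is an extra breakdown that carries its own caveat, every event is also listed individually, and all analyses are descriptive with no between-group safety test in the visible text. All of this stands. It limits the reach of the point, but the column remains non-comparable and the caveat corrects nothing.

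Second, Dose 3 belongs to the HBs-alum regimen, so the overall column compares the regimens as assigned. That also stands: it is a design feature and not an analysis error. The two-dose groups have no scheduled contact between Day 61 and Day 361, while HBs-alum is seen at Visit 8. A reader might infer that fewer events will be found in the two-dose groups and that an AS37 excess could be masked. That is possible, but its size cannot be computed from the documents. Protocol 10.3.4 also tells participants to report medically attended events to the site as soon as possible. A footnote is the proportionate response.

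Third, AS37 is also to be compared with AS03 and AS04, which share its two-dose schedule and contacts. Those comparisons are untouched.

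Fourth, one could argue that Dose 3 is not meant to close the window, since SAP 6.3.3.5 mentions only doses 1 and 2 when it describes the latest dose. SAP 6.3.1 is general, however. On the other reading, the HBs-alum post-Dose 2 column would silently include post-Dose 3 events, which also needs correcting.

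**Conclusion.** The point holds for the by-dose breakdown of SAEs, MAEs and pIMDs at the final analysis, and only for comparisons with HBs-alum. The post-Dose 2 periods differ by a factor of 2.2 (1.9 to 2.6 across the allowed intervals). With equal constant rates, the expected percentage in HBs-alum is about half that of each two-dose group over the assumed range of 0.2 to 1.0 per person-year. If events cluster soon after vaccination, the artefact would be smaller.

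Two stronger readings are tempting and are not supported. One is that the primary safety endpoints are distorted by the window: they are whole-study percentages, nominally over 360 days in every group, and the Day 1-61 tables are unaffected too. The other is that every two-dose group will show double the control's percentage: that is an expectation under assumed rates, and with a handful of events per group the observed order will often differ.

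This is a low-cost improvement to how a known artefact is presented. It does not threaten the primary analysis.

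**What to change.** Amend SAP 4.2.1 before the final analysis:

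1. For the by-dose columns, either report events per person-time at risk, or add a common window from Dose 2 to Day 180 for all groups with HBs-alum censored at Dose 3. Person-time rates compare fairly only if the event rate is roughly constant over time. The common window does not need that assumption.
2. Show HBs-alum post-Dose 3 events in a separate column, and state in 6.3.1 and 6.3.3.5 how Dose 3 is treated.
3. Keep the Day 1-361 table as the primary endpoint, with a footnote that HBs-alum has a third dose and an extra scheduled contact at Visit 8. The common-window table supplements it and should not replace it, because it leaves out the later follow-up.
4. Reconcile the day of Visit 8 (Day 161 in SAP 4.5.1.1, Day 181 in the protocol), and check that the end of the common window agrees with the result.

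The cost is SAP wording and a few tables from dates already collected. No new participant contact is needed. A phone call at about Day 181 in the two-dose groups would be a new protocol procedure and is probably too late, since Protocol Amendment 4 already refers to post-Dose 2 results from all participants.

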#### 4.2.2. Additional considerations

Solicited AEs will be coded by MedDRA (using the latest version) as per the codes in [Table 5](#):

**Table 5      Solicited AEs MedDRA codes**

Solicited symptom	Lower level term code	Lower level term
Arthralgia	10003239	Arthralgia
Chills	10008531	Chills
Diarrhea	10012727	Diarrhea
Erythema	10074796	Administration site erythema
Fatigue	10016256	Fatigue
Fever	10016558	Fever
Headache	10019211	Headache
Loss of appetite	10003028	Appetite lost
Malaise	10025482	Malaise
Myalgia	10028411	Myalgia
Nausea	10028813	Nausea
Pain	10058049	Administration site pain
Swelling	10075107	Administration site swelling
Vomiting	10047700	Vomiting

#### 4.3. Secondary Endpoints Analyses

The analysis of the secondary objective on humoral immune response (anti-HBs antibody concentrations) will be performed on the PPS. The main analysis will be performed on data up to post-Dose 2 (Day 61 – Visit 7) from all cohorts (1-3). The final analysis will be performed on data up to Day 361 (Visit 9). No alpha adjustment is planned for the main analysis.

##### 4.3.1. Within group evaluation

###### 4.3.1.1. Analytical Approach

The within-group evaluation will derive unadjusted GMCs based on the anti-log of the mean of anti-HBs log10-concentrations.

Note: Unless otherwise specified, results below the cut-off of the assay will be replaced by half the value of the cut-off.

95% CIs for GMCs will be based on a back-transformation of student-t CIs for the mean log-transformed anti-HBs antibody concentrations.

[figure not shown]
#### 4.3.1.2. Main Outputs

The following will be tabulated for each group, and at each timepoint that blood samples are collected for the humoral immune response (anti-HBs antibodies):

- Anti-HBs antibody concentrations (at Day 1, 31, 61 and 361):
  - Total N, GMCs and their 95% CI will be tabulated by study group, as well as summary statistics (median, minimum and maximum)
  - GMCs and related CIs by study group will be represented graphically over time. In addition, GMCs over time combining all groups in a single plot will also be produced.
  - Antibody concentrations will be displayed using reverse cumulative curves for each protocol defined timepoint.
- Seroconversion and seroprotection rates (at Day 31, 61 and 361):
  - Percentage of participants above seroconversion and seroprotection threshold will be tabulated with exact 95% CI for each group at each protocol-specified timepoint.

Note: values in graphs will be displayed on the  $\log_{10}$  scale.

[figure not shown]
CC1

[figure not shown]
**CONFIDENTIAL**

215301 (EARLY-CLINRES-017)

CCI

CCI

CCI

## 4.5. Safety Analyses

The main safety analyses are described in Section [4.2](#)

### 4.5.1. Additional Safety Assessments

#### 4.5.1.1. Vital signs

Vital signs (systolic/diastolic blood pressure, and heart rate) and pre-vaccination temperature reported before each study intervention administration (Visit 1 [Day 1], Visit 4 [Day 31] and Visit 8 [Day 161]) will be summarized by group using descriptive statistics.

#### 4.5.1.2. COVID-19 Assessment

The following analyses will be conducted on COVID-19 data:

- Number and incidence of COVID-19 reported as unsolicited AE and SAE will be tabulated by group with exact 95% CI and categorized by MedDRA SOC and PT.
- Severity and outcome of COVID-19 AEs will be tabulated (number and percentage) by group.
- Summary of study completion with reasons for withdrawal related to COVID-19 will be tabulated by group.

## 4.6. Other Analyses

Not applicable.

## 4.7. Analyses

The list and sequence of analyses is described in Section [1.2.2](#)

## 4.8. Changes to Protocol- Defined Analyses

Not applicable.

## 5. SAMPLE SIZE DETERMINATION

A minimum of 23 (and maximum of 30) participants per group will be enrolled in this study. The target sample size has been reduced from 30 to 23 participants per group for reasons of feasibility, as discussed in Section 4.2.1 of the study protocol. [redacted]

[redacted]  
[redacted]  
[redacted]  
[redacted]  
[redacted].

The sample size is not based on formal hypothesis testing and is typical for this kind of study where a treatment is tested for the first-time in human. [redacted]

[redacted]  
[redacted]  
[redacted]  
[redacted]

The primary objectives of the study are to assess the reactogenicity and safety of each vaccine dose throughout the study. [redacted]

[redacted]  
[redacted]  
[redacted].

[figure not shown]
[redacted]  
[redacted]  
[redacted]

[redacted]

